3.3.2 Dose Limiting Toxicity

DLT will be defined as any of the following events determined by the PI to be related to treatment with ciprofloxacin and etoposide and that constitute a change from baseline irrespective of outcome. For the purpose of dose-escalation decisions and MTD determination, only DLTs that occur during the first cycle of ciprofloxacin and etoposide treatment will be taken into account.

1. Any Grade > 3 non-hematologic toxicity, except alopecia; and vomiting or nausea uncontrolled by medical management;
2. Any treatment-related effect that results in a subject missing more than 25% of ciprofloxacin or etoposide;
3. Any non-hematologic toxicity considered to be related to ciprofloxacin or etoposide that results in a delay of Cycle 2 by > 14 days;
4. Grade 4 neutropenia (absolute neutrophil count < 500/mm³) in subjects with baseline ANC levels > 500/mm³ persisting up to 42 days after the start of treatment, in the absence of leukemia;
5. Grade 3 or greater QTc prolongation developing after the start of therapy with oral ciprofloxacin; and/or
6. Any episode of tendon rupture.

For the purpose of dose-escalation/de-escalation decisions and MTD determination, only DLTs that occur during Cycle 1 of Phase Ib will be considered. DLT assessment will occur at the Cycle 1 Day 28 visit. Prior to commencement of Phase II, DLT's and records of toxicity will be reviewed by the DISC.

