Phase Ib:

In the **Phase Ib** portion of the study, subjects will be enrolled in cohorts of three (3) in a traditional 3+3 study design (5). The starting dose is level “0” and includes: ciprofloxacin 750 mg orally twice daily on Days 1 - 10 and etoposide 200 mg orally once daily on Days 2 – 8. During the first cycle of treatment, subjects will be individually assessed for safety and dose limiting toxicity (DLT) for the purpose of determining the MTD of ciprofloxacin. The MTD will be defined as the highest dose of ciprofloxacin at which < 33% of the subjects treated at a given dose level experience a DLT (See [Figure 1](#)). The **Phase Ib** portion of this study ends when a MTD is identified among the three planned dose levels (See [Table 2](#)).

Subjects withdrawn before Cycle 1 Day 1 (C1D1) will not be evaluable for dose escalation decisions and will be replaced in their treatment cohort. A subject is evaluable for dose-escalation decisions provided: they receive all drug doses and remain on study until evaluation at Cycle 1 Day 28 without a DLT; or they experience a DLT during Cycle 1. Subjects who miss any etoposide or ciprofloxacin doses or withdraw from study without a DLT and prior to Cycle 1 Day 28 are not evaluable for dose escalation decisions and will be replaced in their cohort of treatment.

During dose escalation no more than 3 subjects will be treated simultaneously at any given dose level. The **Phase Ib** portion of this study will not be complete until > 28 days after accrual of the last subject.

Phase II:

Enrollment in the **Phase II** portion of the study will begin once the MTD has been determined. After Cycle 1, subjects with progressive disease will be removed from the study. Other study participants will continue to receive a second 28-day cycle of ciprofloxacin and etoposide at the MTD or until one of the following occurs: disease progression, unacceptable toxicity, consent withdrawal, completion of Cycle 2, or termination of the study.

Dose Limiting Toxicity (DLT)

DLT will be defined as any of the following events that are considered to be related to treatment with ciprofloxacin and etoposide. For the purpose of dose-escalation and MTD determination, only DLTs that occur during the first cycle of oral ciprofloxacin and etoposide will be considered. These include:

1. Any Grade \geq 3 non-hematologic toxicity, except alopecia; and vomiting or nausea uncontrolled by medical management;

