4.1 Etoposide and Ciprofloxacin

Ciprofloxacin will be administered orally twice daily on Days 1 to 10 of each 28-day cycle. Whenever possible, doses should be taken at 0800 hours and 2000 hours. If for some reason the doses are not taken at these times, ciprofloxacin can be taken as late as 6 hours after the scheduled time. If > 6 hours elapses, that dose of ciprofloxacin will be held and not made up. The starting dose will be 750 mg (dose level 0) with escalation to a maximum of 1000 mg (dose level +1) or de-escalation to a minimum of 500 mg (dose level -1).

Etoposide at a fixed dose of 200 mg will be administered orally once daily on Days 2 to 8 of each 28-day cycle. Subjects will be instructed to take etoposide with their morning dose of ciprofloxacin at 0800 hours on an empty stomach. If for some reason the dose is not taken at this time, it may be taken as late as 6 hours after the scheduled time. If >6 hours elapses, that dose of etoposide will be held and not made up.

A medication diary will be given to all subjects and they will be instructed to record the actual times they take both etoposide and ciprofloxacin. Doses missed will be recorded as such. Subjects will be told to call within 12 hours of missing a dose. Subjects will be instructed to bring the diary and any unused medication with them to all study visits. Any unused medication will be disposed of per institutional standard practice.

Subjects in Cycle 1 of Phase Ib who miss any etoposide or ciprofloxacin doses will be considered evaluable only if a DLT occurs. Otherwise they will be removed from the study on Day 28 and replaced in the cohort in which they were treated. Subjects in Phase Ib beyond the first cycle and those in Phase II will be considered evaluable for response if they have received at least one cycle in accord with the protocol. For these subjects non-compliance with dosing will be dealt with at the discretion of the PI.

Standard administration instructions will be given to each subject for ciprofloxacin (*e.g.*, separating administration from dairy products, calcium-fortified juices, sucralfate, antacids, or other medications that contain aluminum, magnesium, calcium, iron, or zinc). Subjects will be advised not to consume grapefruit or grapefruit juice within 7 days prior to starting ciprofloxacin and until 7 days after completion of all doses of ciprofloxacin on study.

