4.4 Management of Toxicity

The National Cancer Institute (NCI) Common Toxicity Criteria for Adverse Events version 4 (CTCAE) will be used to grade toxicity (<http://ctepinfo.nih.gov/>). In Cycle 1 of Phase Ib, any patients developing DLT will be permanently withdrawn from the study.

In Phase Ib and in Phase II, for subjects receiving Cycle 2 or beyond, any toxicity which delays treatment beyond day 42 of a cycle will result in permanent withdrawal of the subject from the study. In addition, toxicity which results in missing more than ½ of all doses of etoposide or ciprofloxacin will result in permanent withdrawal from the study.

The following applies to toxicity occurring in Phase Ib or Phase II except as stated:

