4.4.1 Non- Hematologic Toxicity

For any Grade 3 or greater non-hematologic adverse event (AE), deemed related or possibly related to the study intervention and/or the discretion of the investigator, the subject to stop the study drugs.

Management of non-hematologic toxicities such as nausea, vomiting, mucositis, enteritis, and/or diarrhea will follow institutional guidelines.

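### DLT criterion 1 has two thresholds, Grade > 3 in Section 3.3.2 and Grade >= 3 in the synopsis, so some related Grade 3 events, mainly those after the Day 8 morning doses, count under one text but not the other

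*Combined protocol and SAP*

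**What the plan says.** Criterion 1 appears twice. Section 3.3.2 reads "Any Grade > 3 non-hematologic toxicity, except alopecia; and vomiting or nausea uncontrolled by medical management"; the synopsis reads "Any Grade \geq 3 non-hematologic toxicity, except alopecia; and vomiting or nausea uncontrolled by medical management". Only the inequality differs.

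Other criteria, the same in substance in both lists, catch part of what criterion 1 might miss:

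- Criterion 2: "Any treatment-related effect that results in a subject missing more than 25% of ciprofloxacin or etoposide" doses.
- Criterion 3: a related non-hematologic toxicity "that results in a delay of Cycle 2 by > 14 days".
- Criterion 5: QTc prolongation of Grade 3 or more.
- Criterion 6: tendon rupture at any grade.

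Three rules give the classification its consequences. Section 4.4 says that in Cycle 1 of Phase Ib "any patients developing DLT will be permanently withdrawn from the study". Section 4.1 says that Phase Ib subjects in Cycle 1 "who miss any etoposide or ciprofloxacin doses will be considered evaluable only if a DLT occurs"; otherwise they are replaced. Section 4.4.1 has its own drug-stop rule, which begins "For any Grade 3 or greater non-hematologic adverse event (AE), deemed related or possibly related to the study intervention". It uses Grade 3, but it does not define a DLT.

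**The concern.** The maximum tolerated dose (MTD) is the Phase Ib primary objective and fixes the Phase II dose. It is found by counting DLTs in cohorts of three or six, so one reclassified subject can change the decision. If the two texts classify the same Grade 3 event differently, the cohort count depends on which page the investigator has open.

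The loss under Section 3.3.2 takes two forms. A subject whose event comes after the last dose, with no dose missed, counts as DLT-free. A subject who missed a dose because of the event is not evaluable and is replaced. The event then leaves the cohort count, although it stays in the safety records.

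A second, smaller gap is in the same sentence. The clause on nausea and vomiting does not say whether a Grade 3 episode that responds to treatment is a DLT.

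**Working it through.** **Which events are affected.** The schedule in Section 4.1 gives 2 x 10 = 20 ciprofloxacin doses (Days 1 to 10) and 7 etoposide doses (Days 2 to 8) per cycle. Criterion 2 needs more than 25% missed, that is, at least 6 of 20 or at least 2 of 7. If a related Grade 3 event stops both drugs for good, as Section 4.4.1 directs:

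| Both drugs stopped | Ciprofloxacin missed | Etoposide missed | Criterion 2 |
|---|---|---|---|
| Before Day 7 morning | 8/20 = 40% | 2/7 = 28.6% | met |
| Before Day 8 morning | 6/20 = 30% | 1/7 = 14.3% | met |
| After Day 8 morning | 5/20 = 25% | 0/7 | not met |
| Before Day 10 evening | 1/20 = 5% | 0/7 | not met |
| After Day 10 evening | 0/20 | 0/7 | not met |

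Early events that stop both drugs are therefore DLTs under either threshold. The conflict is mainly about events from the evening of Day 8 to Day 28. Within that window, criterion 5 still catches Grade 3 QTc prolongation and criterion 6 catches tendon rupture. Criterion 3 helps little when the dose decision is made: DLTs are assessed at the Day 28 visit, before a delay of more than 14 days can be known.

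**Effect on the 3+3 rule (Section 3.3.1).** Suppose one event is not counted and the subject, or the replacement, has no other DLT. Then 1/3 (expand) becomes 0/3 (escalate), and 2/6 (MTD exceeded) becomes 1/6 (escalate).

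**Reproducing Appendix D.** With DLT probability p, P(escalate) = (1-p)^3 + 3p(1-p)^5. This gives 0.906 at p = 0.10, 0.709 at 0.20, 0.434 at 0.33 and 0.172 at 0.50. Appendix D prints 0.91, 0.71, 0.43 and 0.17. All ten of its values agree to two decimals.

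**Scale of the conflict.** The documents give no rate for the affected events, so these inputs are assumptions:

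- p0 is the rate of DLT by every route that counts under both texts, taken as 0.10 or 0.20.
- x is the rate of related Grade 3 non-hematologic events not caught by criteria 2, 3, 5 or 6, taken from 0 to 0.10 and as independent of p0.

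Under Section 3.3.2, p = p0. Under the synopsis, p = p0 + x(1-p0). For p0 = 0.10 and x = 0.05, p = 0.10 + 0.05 x 0.90 = 0.145, and P(escalate) = 0.855^3 + 3 x 0.145 x 0.855^5 = 0.625 + 0.199 = 0.824.

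| x | p0 = 0.10: Section 3.3.2 | Synopsis | p0 = 0.20: Section 3.3.2 | Synopsis |
|---|---|---|---|---|
| 0 | 0.91 | 0.91 | 0.71 | 0.71 |
| 0.02 | 0.91 | 0.88 | 0.71 | 0.67 |
| 0.05 | 0.91 | 0.82 | 0.71 | 0.62 |
| 0.10 | 0.91 | 0.73 | 0.71 | 0.54 |

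The Section 3.3.2 columns treat affected subjects as DLT-free. If all of them missed a dose and were replaced, the rate among evaluable subjects would be p0/(1 - x(1-p0)). At x = 0.05 this is 0.1047 or 0.2083, and P(escalate) is 0.90 or 0.69, so the gap is nearly the same.

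**The nausea and vomiting clause.** Take its natural sense, that uncontrolled nausea or vomiting is a DLT. A controlled Grade 3 episode is then not a criterion 1 DLT under the Section 3.3.2 threshold. Under the synopsis threshold it is a DLT if the clause adds to the general rule, and not a DLT if the clause means that nausea and vomiting count only when uncontrolled. Moving to Grade >= 3 therefore makes this question live in both places.

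**The case against.** The strongest objection is that there may be no conflict. The sign in Section 3.3.2 could be an underlined > whose bar was lost in PDF reading. The synopsis, the Section 4.4.1 stop rule and the Grade >= 3 safety objective in Section 2.2 all point to Grade >= 3 as the intent. Against that, the same text keeps the >= sign elsewhere, for example in the inclusion criteria. The documents cannot settle it, and anyone with the source file can check it at once. The nausea and vomiting wording is in both places and does not depend on the sign.

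The second objection is that the safeguards bound the harm. This largely stands. Section 4.4.1 protects the individual subject at Grade 3 whatever the DLT label. Early events that stop both drugs are caught by criterion 2. A single DLT among the first three only expands the cohort. Before Phase II, "records of toxicity will be reviewed by the DISC". That review does not repair the count, however: the documents do not require it before each escalation step.

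A reader might go further and infer that the sentence exempts uncontrolled nausea and vomiting along with alopecia. The grammar allows this, but the documents give it no support. With the synopsis threshold it would count controlled Grade 3 vomiting and excuse uncontrolled vomiting, which makes no clinical sense.

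A reader might also take the 2/14 rate of Grade 3 nausea or vomiting in Section 1.2 as an estimate of x. It comes from 100 mg daily for 14 days without ciprofloxacin and covers one toxicity. Neither control status nor timing relative to criterion 2 is given. It cannot serve as an estimate.

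**Conclusion.** The point holds as an inconsistency in the rule that Phase Ib counts by, subject to the caveat about the printed sign. It affects related Grade 3 non-hematologic events that criteria 2, 3, 5 and 6 miss, mainly those after the Day 8 morning doses. It would be wrong to conclude that Section 3.3.2 ignores all Grade 3 toxicity.

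At the assumed rates of 10% by other routes and 5% affected, the gap in P(escalate) is 0.906 - 0.824 = 0.082, about 8 percentage points at one dose level. It is zero if no such events occur, and about 18 points (0.906 - 0.730) at an assumed 10%. These figures show scale and do not predict this trial. Nothing in the documents shows that an unsafe dose would be chosen. The nausea and vomiting gap is secondary: the natural reading counts uncontrolled events, and only the status of controlled Grade 3 events is left open.

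**What to change.** Use Grade >= 3 in both Section 3.3.2 and the synopsis; this agrees with the synopsis as printed and with the Section 4.4.1 stop rule. Split the sentence in two, for example: *Any related non-hematologic toxicity of Grade >= 3, other than alopecia, is a DLT. Nausea or vomiting that medical treatment does not control is also a DLT.* The sponsor should then add one line saying whether controlled Grade 3 nausea or vomiting is exempt. That is a clinical choice, and the documents do not make it.

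The cost is a short text change in two places, with no change to sample size, visits or data collection. The downside is that slightly more events count as DLTs than under the Section 3.3.2 text, so escalation becomes slightly less likely.

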	
 2. Any treatment-related effect that results in a subject missing more than 25% of ciprofloxacin or etoposide doses; 3. Any non-hematologic toxicity considered to be related to ciprofloxacin or etoposide that results in a delay of Cycle 2 by > 14 days; 4. Grade 4 neutropenia (absolute neutrophil count < 500/mm³) in subjects with baseline ANC levels > 500/mm³ persisting up to Day 42 after the start treatment, in the absence of leukemia; 5. Grade 3 or greater QTc prolongation developing after the start of therapy with oral ciprofloxacin; and/or 6. Any episode of tendon rupture. 
Prior to commencement of Phase II, DLT's and records of toxicity will be reviewed by the Data Integrity and Safety Committee (DISC).

Inclusion/ Exclusion Criteria:
	
Inclusion criteria - All of the following must apply:
 
 A. Age ≥ 18 years. B. Diagnosis of AML confirmed by review of bone marrow pathology at the University of Florida. C. Patients with relapsed and or refractory AML 
 • who failed to achieve CR or CRi after at least one cycle of induction chemotherapy and not suitable for second cycle of standard intensive chemotherapy, • who have progressed after 1 cycle of HMA or intolerant to HMA therapy and not suitable for standard induction chemotherapy regimens. • who have relapsed after any duration of response, D. Per the treating physician, the subject must have a life expectancy of ≥ 4 weeks. E. Subject performance status must be ECOG 0, 1, or 2 (See Appendix B). F. Subject must have a total bilirubin ≤ 2 mg/dL and AST and ALT ≤ 2.5 times upper limit of normal. G. Subject must have serum creatinine < 2 mg/dL. H. Females of child-bearing potential (i.e., women who are premenopausal or not surgically sterile) may participate, provided they meet the following conditions: 
 ○ Must agree to use physician-approved contraceptive methods throughout the study and for 6 months following the last dose of ciprofloxacin and/or etoposide. Adequate forms of contraception are abstinence, double barrier methods (e.g., condoms with spermicidal jelly or foam and diaphragm with spermicidal jelly or foam), oral, depot, or injectable contraceptives, intrauterine devices, and tubal ligation. ○ Must have a negative serum pregnancy test within 7 days prior to beginning treatment on this study.

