 - BUN, creatinine, uric acid, total bilirubin, AST, ALT, alkaline phosphatase, LDH, sodium, potassium, calcium, magnesium, phosphorous, bicarbonate, chloride, glucose, albumin, and total protein.

Cycle 1 Day 28

The C1D28 visit may occur \pm 48 hours from the protocol-specified date. All subjects will have the following procedures:

- Document concomitant medications and transfusions;
- AE assessment;
- Physical exam;
- Vital signs, including blood pressure, pulse, respirations, and temperature;
- Weight;
- 12-lead electrocardiogram (ECG), including rhythm, heart rate, and PR, QRS, and QTc intervals;
- ECOG Performance Score;
- Hematology laboratory evaluations:
 - Complete blood count (CBC) including hemoglobin, hematocrit, white blood cell (WBC) absolute differential including circulating blasts, and platelet count;
- Blood chemistry laboratory evaluations:
 - BUN, creatinine, uric acid, total bilirubin, AST, ALT, alkaline phosphatase, LDH, sodium, potassium, calcium, magnesium, phosphorous, bicarbonate, chloride, glucose, albumin, and total protein;
- Bone marrow aspirate and/or biopsy for clinical classification (cellularity, blast assessment) and cytogenetic testing, ; and
- Serum or urine pregnancy test – if applicable for females of childbearing potential.

At C1 D28, the subject will have completed protocol-specified treatment for Cycle 1. For subjects in Phase Ib, DLT assessment will occur at this point.

Cycle 2/Days 1, 8, 15, and 22

All subjects will have the following procedures completed on the visit, unless otherwise specified:

- Document concomitant medications and transfusions;
- AE assessment;
- Physical exam;
- Vital signs, including blood pressure, pulse, respirations, and temperature;
- Weight;
- ECOG Performance Score;
- Hematology laboratory evaluations (unless performed in the 24 hours prior to visit):
 - Complete blood count (CBC) including hemoglobin, hematocrit, white blood cell (WBC) absolute differential including circulating blasts, and platelet count; and

- Blood chemistry laboratory evaluations (unless performed in the 24 hours prior to visit):
 - BUN, creatinine, uric acid, total bilirubin, AST, ALT, alkaline phosphatase, LDH, sodium, potassium, calcium, magnesium, phosphorous, bicarbonate, chloride, glucose, albumin, and total protein.

Cycle 2 /Day 28 (± 2) and EOT (± 7)

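### Two DLT criteria mature at about Day 42, but DLT status is read at Cycle 1 Day 28 and no readable text holds the Level 0 to +1 decision for an open event

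*Combined protocol and SAP*

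**What the plan says.** **What counts as a DLT.** In Section 3.3.2, criterion 3 is a related non-hematologic toxicity that "results in a delay of Cycle 2 by > 14 days". Criterion 4 is Grade 4 neutropenia in a subject with baseline ANC above 500/mm³, "persisting up to 42 days after the start of treatment, in the absence of leukemia". The synopsis has the same limit ("persisting up to Day 42 after the start treatment"). Only DLTs in Cycle 1 count towards escalation and the MTD.

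**When it is read.** Section 3.3.2 says "DLT assessment will occur at the Cycle 1 Day 28 visit". Section 6.2, under Cycle 1 Day 28, says "For subjects in Phase Ib, DLT assessment will occur at this point". The synopsis and Sections 3.3.1 and 11.2.2 make a subject evaluable who has taken all doses and can "remain on study until evaluation at Cycle 1 Day 28 without a DLT". A second limb also makes evaluable anyone with a DLT during Cycle 1; that limb names no day.

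**What happens after Day 28.** Under Section 4.2, a subject with ANC below 500 and marrow cellularity below 5% has treatment held, with weekly CBCs to Day 42 and withdrawal if the marrow has not recovered. Section 4.4 withdraws a subject whose toxicity delays treatment past Day 42 of a cycle. The synopsis adds that the Phase Ib "portion of this study will not be complete until > 28 days after accrual of the last subject". Before Phase II, DLTs and "records of toxicity will be reviewed by the DISC".

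**The concern.** Two of the six criteria mature about two weeks after the visit at which DLT status is read. A subject who at Day 28 has unresolved Grade 4 neutropenia, or a toxicity already holding up Cycle 2, has no DLT yet but may have one by Day 42. On the text, that subject has reached the Day 28 evaluation without a DLT and can enter the cohort count as DLT-free.

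The error runs one way. A true 1/3 counted as 0/3 opens Level +1 instead of adding three subjects at Level 0. A true 2/6 counted as 1/6 escalates past a dose that the rule calls too toxic. The people exposed are the first subjects at ciprofloxacin 1000 mg twice daily. The Appendix D probabilities assume that every DLT is known when the decision is made.

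**Working it through.** **Timing.** Cycle 1 lasts 28 days, so a Cycle 2 delay of more than 14 days is complete only after about 28 + 14 = Day 42. Criterion 4 names Day 42 directly. Both fall about 14 days after the DLT assessment.

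**Search for a hold.**
- The escalation steps in Section 3.3.1 name no wait for an open event.
- The three-subject limit (synopsis, Section 3.3.1) restricts accrual within a dose level, not the opening of the next.
- The period of more than 28 days for completing Phase Ib is a minimum, and shorter than 42 days.
- The Day 42 rules in Sections 4.2 and 4.4 govern that subject's own treatment.
- DISC review of DLTs is required before Phase II. Semi-annual monitoring (Sections 9.3 and 10) and SAE reporting (Section 8.4.1) are not tied to escalation.
- Figure 1 could not be read.

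**The plan's own figure.** With true DLT rate p, P(escalate) = (1-p)^3 + 3p(1-p)^2(1-p)^3. This gives 0.709 at p = 0.20, 0.434 at 0.33 and 0.309 at 0.40, matching Appendix D (0.71, 0.43, 0.31). All ten columns reproduce.

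**Effect of late DLTs.** Let s be the share of DLTs that can be established only after Day 28. The documents give no value, so 5%, 10% and 25% are assumptions. Let e = p(1-s).

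*Worst case: three subjects enrolled together, all still open at the decision.*
- Late DLTs in the first three known by the six-subject decision (those subjects are then at 28 + 28 = Day 56 or later): (1-e)^3 + 3e(1-p)^2(1-e)^3.
- Late DLTs never counted: (1-e)^3 + 3e(1-e)^5.
- Example, p = 0.33, s = 10%: e = 0.297. The first gives 0.347 + 0.139 = 0.486; the second gives 0.347 + 0.153 = 0.500.

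*Staggered accrual.* Phase Ib has 8-24 subjects and Phase II 30 (Section 11.1) to 44 (Section 3.1, Number of Subjects), so 38 to 68 in about 48 months. That is 0.8 to 1.4 a month, a mean gap of about 38 to 21 days, assumed to hold in Phase Ib too. With even gaps above 14 days, only the last subject of each three is still open at that subject's Day 28. Then, with late DLTs in the first three known by the six-subject decision:
- A = (1-p)^2(1-e), the chance that three subjects show no DLT at the decision.
- B = (2p+e)(1-p)^2, the chance that the first three have exactly one DLT and it is counted.
- P(escalate) = A + B × A.
- Example, p = 0.33, s = 10%: A = 0.316, B = 0.430, P = 0.316 + 0.136 = 0.451.

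Random (Poisson) arrivals at the same rates, by simulation, give the upper ends of the staggered ranges at p = 0.33.

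| True p | Accrual | No late DLTs | 5% late | 10% late | 25% late |
|---|---|---|---|---|---|
| 0.33 | Staggered | 0.43 | 0.44-0.45 | 0.45-0.46 | 0.48-0.50 |
| 0.33 | Worst case | 0.43 | 0.46-0.47 | 0.49-0.50 | 0.57-0.61 |
| 0.20 | Worst case | 0.71 | 0.73 | 0.74-0.75 | 0.79-0.81 |
| 0.40 | Worst case | 0.31 | 0.34 | 0.36-0.38 | 0.45-0.49 |

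The chance that a cohort of three contains any late DLT is 1 - (1-ps)^3. At p = 0.33 that is 0.05, 0.10 or 0.23.

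**The case against.** The best defence is that the protocol already treats a delayed cycle as running to Day 42 (Sections 4.2 and 4.4). A late event then falls within Cycle 1, and the second evaluability limb, which has no day, captures it. This stands as far as it goes. A reader might infer that the protocol excludes late DLTs from the count, or that Level +1 must open at Day 28. The documents say neither. What remains is that nothing requires waiting for an open event or says how to revise a decision already taken.

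A reader might also infer that nobody would see the event. That goes too far: SAEs reach the project office within 24 hours and the DISC within 5 days, and the DISC reviews safety at least twice a year and can recommend suspension. These are safeguards, but none is a condition for escalating.

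On size, the objection is largely right. Slow accrual means that earlier subjects will often have passed Day 42 when the third reaches Day 28, which cuts the increase to about half or less. The worst-case figures need near-simultaneous enrolment, which the synopsis permits but the recruitment rate makes unlikely. Exposure is also narrow: one escalation step, with etoposide fixed and only ciprofloxacin rising.

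Finally, Section 4.2 re-treats a subject with ANC below 500 unless cellularity is below 5%, so Day 42 would fall near Cycle 2 Day 14. One might infer that criterion 4 is generally confounded by a second course. That is too broad. The synopsis and Section 3.1 (Overview) give Cycle 2 for stable disease or partial response, whereas criterion 4 requires absence of leukemia. Only the wider wording of Section 3.3.1 on who receives Cycle 2 would let a leukemia-free subject be re-treated.

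**Conclusion.** The point holds and should be fixed. The timing conflict is in the text and depends on no assumption. Subject to Figure 1, which was not available, no text makes the Level 0 to +1 decision wait for an open event.

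The affected group is small: mainly subjects with baseline ANC above 500 and no leukemia who are held for cellularity below 5%, or subjects whose lower-grade non-hematologic toxicity delays Cycle 2. Subjects who have recovered and are on schedule at Day 28 are fully classified then.

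The likely effect on escalation is modest. At a true DLT rate of 0.33 and staggered accrual, it is an increase of about 0.01 to 0.07 over 0.43 across the assumed late shares. The 0.57-0.61 figure is a worst case, not an expectation. Appendix D is computed correctly; it simply presumes complete DLT information.

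**What to change.** Define the DLT window for criteria 3 and 4 as Cycle 1 including any delay before Cycle 2, up to Day 42. Classify a subject as pending at Day 28 if either applies:
- baseline ANC was above 500 and Grade 4 neutropenia is unresolved;
- Cycle 2 is delayed because of toxicity.

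Hold escalation and Phase Ib closure until each pending event resolves or Day 42 is reached. Align the synopsis and Sections 3.3.1, 3.3.2, 4.2, 6.2, 6.3 and 11.2.2.

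The cost is amendment wording, plus up to about 14 days (42 - 28) for a cohort with an open event. Other cohorts lose no time.
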